9.2 Safety monitoring

We will monitor the incidence of severe toxicity that occurs during the first 2 courses and is associated with the treatment (Grade 4 non-hematologic toxicity with specific exclusion of Grade 4 fever/pyrexia which response to Grade <2 within 72 hours with supportive care, Grade 3-4 Left ventricular ejection fraction decrease, Grade 3-4 Retinal detachment or retinal vein occlusion, Grade 2 pneumonitis, Grade 4 rash, Grade 4 hypertension, or Grade >2 allergic reaction). An early stopping rule will be invoked to pause the study if there is evidence that the observed severe toxicity rate is higher than the acceptable rate of 10%. Specifically, if the lower bound of the two-sided 95% exact CI exceeds 10% then the stopping rule will be triggered. We will monitor severe toxicity continuously, after five subjects are enrolled. Toxicity will be reviewed and if the number of subjects with a severe toxicity is equal or greater than the number indicated in the table below, accrual will be paused. Based on simulations, the stopping rule implies that the probability of early stopping will be 5% if the underlying true toxicity rate is 10%, the probability of early stopping will be 55% if the underlying true toxicity rate is 20%, and the probability of early stopping will be 91% if the underlying true toxicity rate is 30%.

Number of subjects	Trial will be paused if the number of subjects with severe toxicity >=
5-6	3
7-11	4
12-17	5
18-23	6
24-29	7
30-36	8
37-39	9

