For evaluating toxicity, a sample size of 39 provides 86% probability to observe at least one toxicity event when the underlying true toxicity rate is 5%, so that we have good confidence to observe a rare toxicity type. In addition, this sample size provides a reasonable precision on the estimate of the toxicity rate. For example, with 7 observed toxicity events out of 39 subjects, the estimated toxicity rate is 18%, with the 95% exact confidence interval (CI) as 8% - 34%.

Data and Safety Monitoring Plan

This study will be monitored in accordance with a Data Safety Monitoring Plan for Phase II Studies. In brief, the role of the Data and Safety Monitoring Board (DSMB) is to protect the interests of subjects and the scientific integrity for clinical trials. The DSMB will monitor this trial at a frequency determined by the DSMB Chair, but at least twice annually. Approximately 2 weeks before each meeting of the DSMB, the study chair will be responsible for working with the study statistician to prepare study reports for review by the DSMB. The DSMB will provide recommendations to change the study or to continue the study unchanged.

Monitoring and auditing procedures will be followed to ensure that the study is conducted, documented, and reported in accordance with the IRB approved protocol, the International Conference on Harmonization (ICH), Good Clinical Practice (GCP) Guidelines, and applicable regulatory requirements of federal regulations. Verification of eligibility and appropriate documentation of informed consent will be performed for **all** subjects enrolled into the study. Monitoring of timeliness of AE and SAE reporting will be done as events are reported. CRFs for **each** subject enrolled will be monitored for completeness and quality by comparing data in the CRFs to data in the source documents.

EXPERIMENTAL DESIGN SCHEMA

Treatment Schema:

 Day 1:
Begin Cycle

Day 28:
 End of Cycle

A cycle of therapy is 28 days.

Subjects will receive study therapy daily for 28-day cycles.

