3.2 Primary Objectives

- To determine the proportion of subjects with an objective beneficial response to trametinib at the end of cycle 6 using an individualized response criterion based on Radiologic Assessment, Patient Reported Outcomes (PROs) and Clinical Benefit Assessment (CBA).
- To determine the safety of oral trametinib in children and young adults with Ras/MAPK pathway driven VA at the end of 6 cycles.

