10 DOSE MODIFICATION AND MANAGEMENT OF ADVERSE EVENTS

10.1 Dose Modifications

10.1.1 Dose Escalation

Patients with critical illness may be initiated at starting dose of 0.0125 mg/kg with approval of study chair or co-chair. If in the opinion of the site investigator this dose is tolerated may then increase to the standard 0.025 mg/kg dosing. This should take place no later than after 3 cycles of treatment.

0.032 mg/kg dosing: Prior Oncologic dosing in patients less than 6 years of age has demonstrated tolerability in those populations at 0.032 mg/kg dosing. Escalation to 0.032 mg/kg dosing prior to completion of 6 cycles of treatment only after approval of study chair or co-chair.

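### The severe-toxicity pause rule in section 9.2 lists exact grades, so as written it counts Grade 2 pneumonitis but not Grade 3, and no treatment-related death unless it is allergic

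*Protocol*

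**What the plan says.** Section 9.2 of the protocol sets the rule: "We will monitor the incidence of severe toxicity that occurs during the first 2 courses and is associated with the treatment". The qualifying events follow in parentheses:

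- "Grade 4 non-hematologic toxicity with specific exclusion of Grade 4 fever/pyrexia" (the fever exclusion applies if it settles within 72 hours);
- "Grade 3-4 Left ventricular ejection fraction decrease";
- "Grade 3-4 Retinal detachment or retinal vein occlusion, Grade 2 pneumonitis, Grade 4 rash, Grade 4 hypertension";
- allergic reactions above Grade 2.

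Accrual is paused when the number of affected subjects reaches a tabulated limit, from 3 among the first 5 to 6 subjects up to 9 among 37 to 39. The limit is reached when the lower bound of the two-sided 95% exact interval exceeds 10%. The section gives stopping probabilities of 5%, 55% and 91% at true rates of 10%, 20% and 30%.

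Three other places bear on this. Section 10.2.1.1 (non-hematological dose-modifying toxicity) also names Grade 2 pneumonitis, but beside general items for Grade 3 and for Grade 4. Section 11.4.1 has the DSMB review unexpected Grade 3 events and all Grade 4 and 5 events. Sections 4.3.1 and 10.1.1 allow a start at 0.0125 mg/kg and say of the increase to 0.025 mg/kg: "This should take place no later than after 3 cycles of treatment".

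**The concern.** A pause rule should count every event at least as bad as those it names. This list is written in single grades and closed ranges, with one open-ended item (allergic reaction). An event can therefore become more serious and drop out of the count. Pneumonitis shows it most clearly, because section 1.2.2 treats it as an event of special interest. The other gap is a treatment-related death from a cardiac, pulmonary or other non-allergic cause.

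This is the only numerical safety boundary in the trial. If it misses the worst events, the tabulated limits and the quoted stopping probabilities describe something narrower than severe toxicity. The trial enrolls from 2 months of age.

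**Working it through.** **1. The plan's own figures.** For each n from 5 to 39, take the smallest x whose Clopper-Pearson two-sided 95% lower limit exceeds 0.10. All 35 values match the table in section 9.2; for example, 3 of 6 gives a lower limit of 0.118 and 9 of 39 gives 0.111. An exact binomial recursion, looking after every subject from the fifth to the 39th, gives:

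| True rate | Stated | Exact |
|---|---|---|
| 10% | 5% | 6.0% |
| 20% | 55% | 53.4% |
| 30% | 91% | 92.3% |

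Each is within 2 points of a figure the protocol describes as simulated. The boundary is sound.

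**2. The event list, grade by grade.**

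| Event | Grades counted as written | Worse grades not counted |
|---|---|---|
| Pneumonitis | 2 (named), 4 (general item) | 3, 5 |
| LVEF decrease; retinal detachment or vein occlusion | 3, 4 | 5, where the scale assigns one |
| Other non-hematologic toxicity, including rash and hypertension | 4 | 5 |
| Allergic reaction | 3, 4, 5 | none |

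**3. Comparison with section 10.2.1.1.** There the Grade 2 pneumonitis entry lowers the threshold for one event, and the general Grade 3 item, whose exceptions do not include pneumonitis, picks up the next grade. Section 9.2 has the same pneumonitis entry but no general Grade 3 item.

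**4. What this does to the count.** With six subjects enrolled the limit is 3. Three subjects with Grade 2 pneumonitis trigger the pause. Two with Grade 2 and one whose event is recorded as Grade 3 give a count of 2, and accrual continues. Three treatment-related non-allergic deaths with no other counted event give a count of 0.

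**5. Size under an assumed share missed.** Let m be the share of severe toxicities falling in uncounted grades. The documents give no value for m. The counted rate is p(1 − m), passed through the same recursion:

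| True rate p | m = 0 | m = 5% | m = 10% | m = 20% |
|---|---|---|---|---|
| 20% | 0.534 | 0.476 (rate 0.19) | 0.417 (0.18) | 0.302 (0.16) |
| 30% | 0.923 | 0.892 (rate 0.285) | 0.851 (0.27) | 0.740 (0.24) |

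**6. Secondary: window and dose.** The protocol states "A cycle of therapy is 28 days". Reading a course as a cycle, the window is 2 × 28 = 56 days, while the increase from the lower start may come as late as 3 × 28 = 84 days, which is 28 days after the window closes. Suppose a share f of subjects spends the whole window at half dose with half the toxicity rate. The counted rate is then p(1 − f + 0.5f). At p = 30% the pause probability is 0.892 (f = 10%), 0.851 (20%) and 0.801 (30%), against 0.923. At p = 20% it is 0.476, 0.417 and 0.359, against 0.534. Neither f nor the halved rate is in the documents.

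**The case against.** The strongest reply is that this is shorthand. The pneumonitis wording looks carried over from section 10.2.1.1, and nobody would knowingly pause for Grade 2 and ignore Grade 3. A lost at-least sign cannot be excluded either: the age in the pregnancy-test criterion appears with a garbled symbol in the synopsis and none in section 5.1. Both points bear on intent. Against them, the same sentence writes closed ranges for the cardiac and retinal items and an open-ended grade for allergic reaction, so the notation was available. A pause rule has to be applied as it reads.

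The second reply is that deaths are handled elsewhere. Section 11.4.1 requires Grade 4 and 5 events to reach the DSMB within 5 calendar days and lets it terminate the study. Section 10.12 requires fatal or life-threatening events to reach the coordinating center within one business day. This stands, and it makes the three-deaths example unlikely to pass unnoticed. But this review is discretionary and separate from the count. For Grade 3 pneumonitis it is also less certain: the DSMB reviews unexpected Grade 3 events, and section 10.2.6.6 describes pneumonitis as already observed with trametinib.

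A reader might infer that every Grade 5 event is left out. That goes too far, because the allergic item has no upper limit. A reader might also infer from the dose provisions that the 2-course window is itself an error, given a primary objective of "To determine the safety of oral trametinib in children and young adults with Ras/MAPK pathway driven VA at the end of 6 cycles". The documents do not support that. An early window is a legitimate choice for a pause rule, and section 9.3 estimates the toxicity rate separately in all dosed subjects. Nor is toxicity after an increase always missed: a subject raised after cycle 1 has cycle 2 inside the window.

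**Conclusion.** The concern holds for the event list. As written, section 9.2 does not count Grade 3 pneumonitis or any Grade 5 event other than an allergic reaction, so the only quantitative pause boundary can miss events worse than those it names. This rests on reading the printed grades literally; if an at-least sign was intended, the text still needs it. The size depends on how often such events occur, which the documents do not state, so the figures for missed events show sensitivity only. The boundary table is not at fault.

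The dose-window point is a secondary note. It applies to low-dose starters raised after course 2 and to any later escalation. It means that the stated 5%, 55% and 91% describe toxicity in the first 2 courses at the dose actually given, which need not be the standard dose. With 10% to 30% low-dose starters and half the toxicity at half dose, both assumed, the pause probability at a true 30% is about 0.89 to 0.80 against 0.92. That does not by itself require a change of design.

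**What to change.** Amend the event list in section 9.2 so that each item is a minimum grade and nothing worse than a counted event is left out. State explicitly that treatment-related Grade 5 events count. Reconcile the list with sections 10.2.1.1 and 11.4.1. Leave the boundary table as it is.

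Separately, reconcile sections 9.2 and 10.1.1 by saying which dose exposure the 2-course window and the quoted stopping probabilities describe, and whether a course is a 28-day cycle. Restarting the window at each dose increase is not recommended as a simple repair: the table is calibrated to one 2-course window per subject, and repeated windows would no longer match it.

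The cost is a short amendment and an updated monitoring report. The downside is a slightly higher chance of a pause, since more events qualify.

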9.3 Statistical Analyses Plan

For all the analyses, subjects who received any dose of trametinib will be included in the analyses. The primary efficacy endpoint is objective response (including both response and partial response) at the end of cycle 6 and the primary safety endpoint is toxicity of trametinib. We will use binomial distributions to estimate the response and the toxicity rates with their 95% exact CIs. For the second primary efficacy endpoint of responses at the end of cycles 12 and 24, the response rate will also be calculated with 95% CI. For the secondary endpoint of duration of response, time from initial response to disease progression will be examined, and subjects will be censored at the last adequate disease assessment if no progression occurred by that time. We will use the log-rank tests and/or Cox proportional hazard regression to analyze the endpoint. Should the data suggest the violation of the

proportional hazard assumption, we will consider an alternative method such as accelerated failure time model analysis.

Secondary data analyses will be performed for the secondary outcomes of longitudinal measurements of radiologic assessment, PROMIS Patient Reported Outcome measurements, and Clinical Benefit Assessments, taken at screening, and at the end of cycles 6, 12, 18, and 24. The longitudinal data will be analyzed separately at each follow-up time point and together longitudinally. The paired t-test will be used to look at changes in these measures from pre-treatment levels to the post-treatment level (follow-up at cycle 3) to evaluate the treatment's short-term effects. Mixed effects models will be used for longitudinal analysis to evaluate changes in these measures over time. Should the data suggest the distributions of the measurements deviate from normal distributions, we will consider nonparametric alternatives such as Wilcoxon signed rank test or transformation. Relationships between PROMIS measures and other variables such as pain will be investigated using correlation analysis. Lastly, exploratory analyses will be performed for biomarker measures such as cell-free DNA. Descriptive statistics will be generated to summarize data.

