3.3 Secondary Objectives

- To assess the duration of response in subjects receiving trametinib at the end of cycles 12 and 24.
- To assess the proportions of subjects with a response at the scheduled protocol visits for disease evaluation at the end of cycles 12 and 24.
- To assess the changes in symptoms and complications/comorbidities associated with Ras/MAPK pathway driven variants in VA.
- Determine the most common and most serious adverse events as defined by Common Terminology Criteria for Adverse Events (CTCAE, version 5.0) in this vascular anomalies population

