4 INVESTIGATIONAL PLAN

4.1 General Schema of Study Design

This study is a single-arm, open-label investigational Phase II study of trametinib administered orally or by naso- or gastric-tube on a continuous 28-day cycle, for up to 24 cycles in subjects ages 2 months to 30 years with genetically confirmed Ras/MAPK pathway

associated vascular or complex lymphatic anomalies. Subjects in the absence of toxicity and with clinical benefit may continue into the extension period for 36 cycles total.

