8.3.3 Duration of Response

Duration of Overall Response: The overall response (substantial or intermediate) duration is measured from the time of primary endpoint measurement (6 cycles) until the first date that recurrent or progressive disease is objectively documented (taking as reference for progressive disease the smallest measurements recorded since the treatment started).

Duration of Stable Disease: Stable disease is measured from the start of the treatment until the worsening disease criteria are met, or patient on evaluation has a substantial or intermediate response.

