9.1 Sample Size and Power

For the primary efficacy analysis of objective response at the end of cycle 6, we will test a null hypothesis of response of 40% against an alternative hypothesis of response rate of 65%. We will follow the Simon's optimal two-stage design: an interim analysis will be conducted after 16 subjects have been observed for response, and if 6 or fewer response is observed, the trial will be stopped for futility; otherwise the trial will continue to enroll a total of 39 evaluable subjects and at the end of the trial if 20 or more responses are observed, the treatment will be declared promising. This design provides $\geq 90\%$ power when the true response rate is 65% and yields a one-sided type I error of ≤ 0.05 when the true response rate is 40%.

For evaluating of toxicity, a sample size of 39 provides 86% probability to observe at least one toxicity event when the underlying true toxicity rate is 5%, so that we have good confidence to observe a rare toxicity type. In addition, this sample size provides a reasonable precision on the estimate of the toxicity rate. For example, with 7 observed toxicity events

out of 39 subjects, the estimated toxicity rate is 18%, with the 95% exact confidence interval (CI) as 8% - 34%.

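### Section 9.3 analyses duration of response by log-rank and/or Cox methods in a single-arm trial with no group or covariate named, so the stated analysis does not yield the durability at cycles 12 and 24 that the objective asks for

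*Protocol*

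**What the plan says.** - **Design** (Protocol 4.1): "This study is a single-arm, open-label investigational Phase II study of trametinib".
- **Objective** (Protocol 3.3): "To assess the duration of response in subjects receiving trametinib at the end of cycles 12 and 24". The proportion of subjects with a response at those visits is listed as a separate secondary objective.
- **Endpoint in the analysis section** (Protocol 9.3): "time from initial response to disease progression will be examined, and subjects will be censored at the last adequate disease assessment" if there has been no progression.
- **Method** (Protocol 9.3): "We will use the log-rank tests and/or Cox proportional hazard regression to analyze the endpoint". If the data suggest that proportional hazards does not hold, "we will consider an alternative method such as accelerated failure time model analysis".
- **Endpoint in the response section** (Protocol 8.3.3): for a substantial or intermediate response, duration "is measured from the time of primary endpoint measurement (6 cycles) until the first date that recurrent or progressive disease is objectively documented".
- **Response at later visits** (Protocol 9.3): for cycles 12 and 24, "the response rate will also be calculated with 95% CI".

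Section 9.3 ties no subgroup, covariate or historical curve to duration of response. Disease strata are mentioned once, in the dosing text (4.3.1), and genetic variants appear as an exploratory description (3.4). Neither is linked to this analysis.

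**The concern.** The objective is descriptive: among subjects who respond, how long does the response last? The methods named are comparative. A log-rank test asks whether two or more curves differ, and Cox regression estimates the effect of a covariate on the hazard. With one arm and nothing named to compare, the method does not fit the question.

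This is more than detail left to a statistical analysis plan. The protocol positively prescribes the methods. A plan that followed Section 9.3 would carry the mismatch forward, and one that used a one-sample estimate would depart from the stated method. At stake is whether the trial reports a durability figure by a pre-specified route, or whether the method, and possibly the comparison, is chosen after the data are seen.

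**Working it through.** The protocol gives no target duration, event count or hazard ratio for this endpoint, so there is no figure to reproduce. The check is whether the stated methods return the quantity asked for.

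**1. Log-rank with one group.** At each event time j, let d_j be the events, n_j the number at risk, and n_1j the number at risk in group 1. With one event per time:

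- O = Σ d_j
- E = Σ d_j · n_1j / n_j
- V = Σ (n_1j / n_j)(1 − n_1j / n_j)

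With a single group n_1j = n_j throughout, so E = O and V = 0, and the statistic (O − E)/√V is 0/0. A run on one simulated group of 25 responders gave O = 15, E = 15.0, V = 0.

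**2. Cox without covariates.** Each event contributes 1/n_j to the partial likelihood. No parameter appears, so there is no coefficient and no hazard ratio.

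**3. The fallback.** Proportional hazards is an assumption about how a covariate acts on the hazard. Without a covariate there is nothing to violate, so the condition for moving to an accelerated failure time model never arises.

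**4. Do the response rates at cycles 12 and 24 fill the gap?** No. Illustration with 39 subjects: 25 respond at cycle 6; by cycle 12, 5 of them have progressed and 5 others have begun to respond. The response rate is 25/39 = 64% at both visits, yet only 20/25 = 80% of the cycle 6 responders are still in response. The two quantities can move separately.

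**5. What a one-sample estimate would give.** Section 9.1 plans 39 evaluable subjects, sets success at 20 or more responses, and assumes a 65% response rate (0.65 × 39 ≈ 25). Assuming 20 to 25 responders and ignoring censoring, exact 95% intervals for the proportion still in response are:

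| Still in response | Proportion | Exact 95% CI |
|---|---|---|
| 10 of 20 | 50% | 27% to 73% |
| 14 of 20 | 70% | 46% to 88% |
| 16 of 20 | 80% | 56% to 94% |
| 18 of 25 | 72% | 51% to 88% |
| 20 of 25 | 80% | 59% to 93% |

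Censoring would widen these. There could also be fewer responders, because the synopsis counts stable disease among the responses at the interim look, whereas 8.3.3 times only substantial and intermediate responses.

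**6. If subgroups were formed later to make the log-rank usable.** Assume an equal split, a hazard ratio of 0.5 and two-sided 0.05. Power is Φ(½·√d·|ln 0.5| − 1.96) for d events:

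- d = 5: 0.775 − 1.96 = −1.185, power 12%
- d = 10: 1.096 − 1.96 = −0.864, power 19%
- d = 20: 1.550 − 1.96 = −0.410, power 34%

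For 80% power, d = 4(1.96 + 0.842)²/(ln 0.5)² ≈ 65.4, that is 66 events, more than the 39 subjects in the trial.

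**7. Time origin.** Section 8.3.3 starts the clock at the cycle 6 assessment, Section 9.3 at initial response. Under 8.3.3 the two landmarks lie (12 − 6) × 4 = 24 weeks and (24 − 6) × 4 = 72 weeks after the origin. Under 9.3, a subject who first responds at cycle 12 starts the clock there. The durations, and possibly who counts as a responder, differ between the two sections.

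**The case against.** **The methods are not strictly incapable.** Cox regression needs covariates rather than groups, and age or a biomarker level would serve. A Cox baseline survival curve, or an accelerated failure time model with only an intercept, could yield survival probabilities and a median. This stands as a limit on wording: the right statement is that the methods as stated do not yield the figure, not that no use of them could. The protocol names no covariate, does not mention a baseline curve, and brings in the accelerated failure time model only as a remedy for non-proportional hazards.

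**Kaplan-Meier detail belongs in the analysis plan.** A missing estimator alone would be no finding. Here, however, a different and unsuitable method is stated. The promised response rates and descriptive summaries narrow the gap in information but do not measure durability among responders.

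**A stronger reading a reader might infer.** PROs and CBA are scheduled every 6 cycles (24 weeks), so one might conclude that dating progression at the visit biases the result, lengthens every duration, and makes an interval-censored analysis necessary. The documents do not support this:

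- The objective refers to scheduled visits. Rounding an event time T up to the next 24-week visit leaves P(T > 24k) unchanged, so the proportion in response at the cycle 12 and 24 visits is not affected. Imaging, where applicable, is also due at both.
- The abstract, synopsis and treatment schema call for earlier assessment when there are signs of worsening.
- Subjects without progression are censored at their last adequate assessment and are not lengthened. Under the 9.3 origin, late detection of response shortens the measured duration.
- Section 8.3.3 defines the event as the first documented date, which is a conventional choice.

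The median can be affected by visit spacing, but that supports at most an optional sensitivity analysis.

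**Conclusion.** The point holds. In this single-arm trial Section 9.3 prescribes a test that is undefined on one group, or a model with no coefficient to estimate, for an objective that asks how long responses last. That conclusion rests on the text and needs no assumption; only the illustrative intervals and power figures rest on assumed responder counts, event counts and a hazard ratio.

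The consequence is confined to a secondary endpoint: no pre-specified durability estimate, and room to choose the comparison after the fact, with 12% to 34% power in the scenarios shown. The point should be corrected but does not bear on the primary decision rule, the sample size or safety. It does not extend to a claim that visit-date recording distorts the cycle 12 and 24 figures.

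**What to change.** Replace the log-rank/Cox sentence in Section 9.3, and the accelerated failure time sentence that depends on it, with:

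> *Among responders, the proportion still in response at the end of cycles 12 and 24 and the median duration of response will be estimated by Kaplan-Meier with 95% CIs.*

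Keep log-rank or Cox only for exploratory comparisons by factors named in advance, such as genotype, and state that these have little power.

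In the same edit, use one time origin in Sections 8.3.3 and 9.3 (the cycle 6 assessment or initial response) and say that responders are the substantial and intermediate responders of 8.3.3. Without this the Kaplan-Meier estimate is not fully defined. An interval-censored estimate of the median may be added as an optional sensitivity analysis.

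The cost is a short edit to 9.3 and an alignment of 8.3.3. It needs no new data, visits or subjects, and standard software suffices.
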